Randomization: Immediately after completing baseline assessment, small block randomization (via REDCap) will create groups balanced on age and on the proportion who identify as nHBAM. We estimate that 90% of those enrolled will be nHBAM. 72 participants will provide sufficient power for the analyses (see Data Analysis). Recruitment will continue until 72 nHBAM are enrolled.

Format: Immediately after randomization, participants (adolescents and parents/caregivers) in the active (MySTYLE) condition will receive two secure, HIPAA compliant texts or emails to their mobile phones or preferred indicated device each week for eight weeks and each text/email will contain a link to new media content (overall, at least 120 minutes of multimedia time is planned, not including participant replays, which is comparable to our interactive DVD and to an online RCT conducted by Mustanski and colleagues). (9) The weekly content, as well other content and interactive materials, will be available on their condition's secure website. All nHBAM and enrolled parents/caregivers will each have their own links with separate, but parallel, content (see Figure below in Intervention Conditions). Those participants assigned to the waitlist will be eligible to participate in MySTYLE after they have completed their 2- and 4-month assessments. They then will receive two secure, HIPAA compliant texts or emails to their mobile phones or preferred indicated device each week for eight weeks and complete further assessments at 6 and 8 months. If those enrolled in the waitlist choose to participate in MySTYLE, they will have the opportunity to include their parent mid-intervention. During the 4 months that the participant is on the waitlist, study staff will not engage with the parent.

Intervention fidelity and usage: The twice-weekly video/graphic content will be embedded in the participant's unique REDCap link, providing data on the number of videos viewed by each participant. The participant will not proceed to the next web page (containing options for their weekly practice, etc.) until the video has fully played, but it may be paused and resumed later. The videos/graphics will be posted on the website for repeat viewing. Analytics will be collected on the number of minutes enrolled nHBAM spend viewing project materials, the content accessed, and the number of times any one video was re-played.

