
Location: Assessments of adolescents at baseline, 2 months, 4 months, and 6 months (waitlist only) and 8 months (waitlist only) will occur in person in a safe, convenient location at the Jackson Medical Mall or the Jackson Medical Tower. Both locations are easily accessible and used by the entire community, which avoids stigma. **Mode**: REDCap is a CASI system that is HIPPA-compliant and meets HITECH security and privacy requirement (Appendix 4).

Parent/Caregiver Outcomes. All assessments for parents/caregivers will occur online, using the same REDCap software provided to adolescents. Parents will complete a parental version of all eight Family and Relationship scales in Table 1 (there is separate adolescent version of each scale), as well as measures of acceptability at 2 or 6 months (CSQ) depending on assigned condition.

Table 1. Social Personal Framework Factors, Intervention Targets, Measu

Social Personal Framework factors		Intervention	Measures
	HIV Knowledge	HIV Facts	HIV Knowledge Scale ⁽⁷⁹⁾

Personal	PrEP Knowledge	PrEP Facts	PrEP Knowledge Scale
Attributes	_		Homophobia Scale
			(Wright et al., 1999) Genderism and
	Internalized Stigma,		Transphobia Scale
	Homophobia,		(Tebbe, Moradi, & Ege
	Transphobia	Information, Motivation	2014)
Risk Behaviors	Youth Risk Behaviors	Motivation, Skills	YRBSS (CDC 2017)
	Substance Use	Motivation, Skills	ASSIST ⁽⁹¹⁾ ;
	Sexual Risk Behaviors	Motivation, Skills	ARBA ⁽⁷⁶⁻⁷⁸⁾
Family* A=adolescent P=parent	Acceptance of	Self-safety Evaluation,	(00)
	Sex/Gender	Motivation	Acceptance Items ⁽⁹²⁾
			Silverberg Scale (PPM) (94, 95) A/P
	Denouties Desetions	Information, Skills (e.g.	Intervention Practice
	Parenting Practices	monitoring of peers)	exercises A/P Parent-Adolescent
	Communication about		Sexual Communication
	Sex	Assertive Skills	Scale ⁽⁹⁷⁾ A/P
			Parent Knowledge of PrEP item; Acceptance
	PrEP Items for		of son taking PrEP item
	Parents	Motivation	Р
Relationship		Motivation, Assertive	
Concerns	Family Support	Skills	MSPSS ⁽⁹⁸⁾ A/P
A=adolescent P=parent	Significant Non-family Adult Support	Motivation, Assertive Skills	Social Support ⁽⁸³⁾ A/P
i paront	Tradit Oupport	Knowledge, Coping	Coolai Capport Air
Community	a. Stigma	Skills	Cultural Stigma ⁽⁹⁹⁾
		Knowledge, Assertive	
	b. Healthy Resources	Skills	Resources Checklist

^{*}The measures for this construct include both parent (P) and adolescent (A) forms

POST-TEST INTERVIEWS

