Parents/caregivers in the pilot and randomized trial phases will complete questionnaires about their demographic information, parenting practices, parental monitoring, parent-teen communication about sex, acceptance of another's non-heterosexual orientation, social support, and measures of acceptability. During the trial phases, all assessments for parents/caregivers will occur online.

Linkages to Subjects and Access to Subject Identities

For each stage of the research study, participant names and contact information will be maintained in a recruitment/enrollment database. Once individuals enroll in the study, names will be linked to a participant ID number in this database, which will be kept in a restricted access folder on a secure server. All name/ID number files will be assigned a code name unrelated to the name of the study. Signed consent and assent forms will also be kept in a locked file cabinet, separate from any other project data. Once data collection is completed, the corresponding recruitment/enrollment database will be deleted as it is unnecessary to maintain the link between participant identity and study data. Destruction of these databases must be witnessed and documented on the Master List Verification of Destruction document, which will be maintained in a regulatory file. Furthermore, any information collected as part of this study will be accessible only to research staff that has completed mandatory training in the protection of human subjects.

Potential Risks

The risks for this study are considered minimal. Every effort will be made to ensure that study participants are protected from risks. The risks are as follows: 1) potential coercion; 2) loss of confidentiality; 3) emotional discomfort during the assessments and/or intervention activities; 4) risk associated with learning they have HIV, if that is diagnosed during the course of the study; and 5) adverse reactions from parents/caregivers if participant discloses sexual attitudes or behavior (disclosure is not a study requirement). The protection against each risk is described in detail below under Adequacy of Protection Against Risk.

Adequacy of Protection Against Risk

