Importance of Knowledge to be Gained. All phases of the proposed study will provide important information for the development of HIV prevention interventions for non-heterosexual Black adolescent males. We hope that our intervention will be successful in reducing HIV risk behavior among non-heterosexual Black adolescent males and think that the clear examination of these questions outweighs the previously mentioned risks. The effectiveness of a tailored, scalable, online HIV prevention intervention is severely understudied with this population. Given the significant risk of HIV infection among nHBAM and the lack of easily accessible prevention interventions tailored specifically to nHBAM, the knowledge to be gained from this research is significant. The risks to participants are reasonable in relation to the importance of the knowledge to be gained.

Reimbursement for Time and Effort. Participants (approximately 15 non-heterosexual Black adolescent males, 15 parents/caregivers) will be reimbursed \$30 for focus group participation. Stakeholders will be reimbursed \$50 for focus group participation. Community Advisory Board members (4 non-heterosexual Black adolescent males, 4 parents/caregivers, 4 community members) will be reimbursed approximately \$50 for each meeting (12 CAB members x \$50 x 4 meetings/year in Years 1-3). Participants in the Open Trial (10 nHBAM and their parents/caregivers) will be reimbursed \$35 for the baseline and 2-month post-intervention assessments. Randomized Controlled Trial participants (72 nHBAM) will be reimbursed approximately \$35 for the in-person assessments (baseline, 2-months, 4-months, 6-months and 8-months post-intervention). Only those assigned to the waitlist control condition will be eligible for the 6- and 8- month assessments. Randomized Controlled Trial parents/caregivers will be reimbursed \$35 for each of the online assessments (baseline, 2-months, 4-months, 6-months and 8-months post-intervention). Only those assigned to the waitlist control will be eligible to complete the 6- and 8-month assessments. All online assessments will culminate in a screen that provides study participants with a code for an online purchase from Amazon.com. Currently enrolled participants will be incentivized to recruit up to five new participants and will receive an

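### Staff may not engage waitlist parents for 4 months, yet trial parents are paid for surveys at 2 and 4 months; if the bar covers surveys, parent self-report has no randomised comparison

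*Combined protocol and SAP*

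**What the plan says.** Three parts of the protocol decide when waitlist parents are measured.

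- **Format (RCT phase).** Waitlist families may take MySTYLE after the 4-month assessment. If they do, "they will have the opportunity to include their parent mid-intervention". The next sentence reads: "During the 4 months that the participant is on the waitlist, study staff will not engage with the parent".
- **Reimbursement for Time and Effort.** Trial parents are paid "for each of the online assessments (baseline, 2-months, 4-months, 6-months and 8-months post-intervention", with a single arm restriction: "Only those assigned to the waitlist control will be eligible to complete the 6- and 8-month assessments". Nothing limits baseline, month 2 or month 4 to the active arm.
- **Parent entry.** Parent or caregiver enrollment (RCT phase) lets a parent start at study entry, at mid-intervention or straight after the 8 weeks, and gives the parent the adolescent's condition. RCT enrollment (human subjects section) lists only the first two entry points. Neither names an arm. Under items d and e of the RCT-phase list, adolescents who at first declined are asked again midway and at the end, and any change of mind is credited to the intervention.

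On what is compared, the Specific Aims place parental attitudes and behaviour among the Aim 3 effect sizes, and the Aim 3 statement in the RCT phase sets MySTYLE against waitlist for adolescents and their parents. Parent/Caregiver Outcomes gives parents their own versions of the family and relationship scales, notes that "there is separate adolescent version of each scale", and dates only the "measures of acceptability at 2 or 6 months (CSQ) depending on assigned condition". Sources of Material adds that "During the trial phases, all assessments for parents/caregivers will occur online", without time points.

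**The concern.** The meaning of *engage* settles whether control data on parents exist. Staff who follow the Format sentence to the letter would send nothing to waitlist parents at months 2 and 4, and those data could not be recovered later. Staff who follow the payment list would survey both arms.

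The product of this pilot is a set of effect sizes for a larger application. Without waitlist parents, a parent self-report effect size would be an uncontrolled change in self-selected active-arm parents, although Aim 3 presents it as a comparison with waitlist.

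A second question arises whichever rule governs. Active-arm families get further chances to bring a parent in during and just after the intervention. The Format section gives waitlist families no such chance before month 4. The plan does not say how the later-joining parents are analysed.

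**Working it through.** **Time scale (assumption).** Months are counted from baseline, as in Measures for the Randomized Trial. The payment list adds a post-intervention label to a series that begins at baseline; I read that series as months from baseline too.

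**Step 1. Parent survey months under each reading.**

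| Reading | Active arm | Waitlist arm | Shared follow-ups |
|---|---|---|---|
| Payment list governs | 0, 2, 4 | 0, 2, 4, 6, 8 | 2 and 4: 2 of 2 |
| Format rule covers surveys | 0, 2, 4 | 0 if enrolled before randomisation; 6, 8 | none: 0 of 2 |

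A parent baseline completed before randomisation breaches neither rule, since the arm is not yet known. The Randomization section says "Immediately after completing baseline assessment, small block randomization (via REDCap) will create groups balanced", without saying whose baseline.

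**Step 2. Can months 6 and 8 stand in?** A waitlist parent who joins midway through the delayed course enters at 4 months + 4 weeks = 4 + 28/30.4, or about 4.9 months. Both later surveys then follow the start of exposure, and the active arm has no parent surveys at those months. They supply no between-arm contrast.

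**Step 3. Later-joining parents.** In the active arm, mid-intervention is 28/30.4, or about 0.9 months, and end of intervention is 56/30.4, or about 1.8 months. Such a parent can supply at most months 2 and 4 (2 of 3 assessments) and has no pre-randomisation baseline. The Format section's equivalent for waitlist is about month 4.9. A between-arm comparison that included these parents would therefore mix families present at randomisation with families selected afterwards in one arm only, partly by the intervention itself.

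**Step 4. What is touched.** The three behavioural outcomes (condomless sex acts, onset of sexual activity, HIV test acceptance) come from adolescents. So do the adolescent versions of the family scales. Adolescents in both arms are assessed at baseline, 2 and 4 months, so these comparisons stand. Only parent self-report is at issue.

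**Step 5. Sample for the parent comparison.** The plan gives no parent participation rate, and its detectable effects do not bear on the conflict. For scale only, assume 1:1 allocation (not stated), the Power section's 85% retention, and a proportion *p* of families in each arm whose parent completes baseline before randomisation. Parents per arm = 36 × 0.85 × *p* = 30.6 × *p*:

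- *p* = 25%: about 8
- *p* = 48%: about 15
- *p* = 75%: about 23
- *p* = 100%: about 31

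The 48% is the share of adolescents in a cited study who were willing to have caregivers contacted. It is a reference point, not an estimate for this trial.

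**The case against.** The sections can be read together. The rule sits under Format, which is about content delivery, directly after the sentence on including a parent mid-course. Elsewhere (items d and f of the RCT-phase list, and the opening note of the human subjects section) engaging a parent means bringing one into the study. The rule may therefore mean only that staff will not recruit or involve parents during the wait. Format also opens by counting parents among its participants, then has waitlist participants complete 2- and 4-month assessments, although its later wording points back to adolescents. Parent surveys are online and survey invitations are automated, so little staff contact is needed. The payment list is not an assessment schedule, and its time labels are loose. The enrolment schematic and the measures appendix are not available here. Finally, this is a pilot, and its behavioural outcomes are all adolescent ones.

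Much of this stands. A reader might infer that the plan leaves waitlist parents unmeasured; the text does not establish that. But no visible sentence adopts the reconciled reading, and the same usage cuts the other way: if an engaged parent is one who takes part, a parent who is not engaged may be taken not to be surveyed.

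Other stronger inferences also fail:

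- That family outcomes lose their randomised comparison altogether. The adolescent-report scales keep it.
- That later-joining parents do bias the comparison. That depends on their being pooled, which the plan does not state.
- That the PrEP items are lost because only parents answer them. This rests on a table broken in extraction and conflicts with the statement that every scale has an adolescent version.

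**Conclusion.** The conflict is real and should be fixed, within a narrow scope. If the no-engagement rule covers surveys, the follow-up points at which parents can be compared between arms fall from 2 of 2 to 0 of 2, and no sample size restores the parent self-report comparison that Aim 3 promises. If it does not, a clean comparison exists for parents enrolled with a baseline before randomisation. Later joiners are selected after randomisation under both readings, and pooling them could bias the result.

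This rests on the visible text and on counting months from baseline. Delaying parent involvement is a deliberate protection for adolescents and is not questioned. Nor does the point show the Power section's figures to be wrong: that section does not say whose report of family practices it covers.

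**What to change.** Reconcile Format, Parent or caregiver enrollment, RCT enrollment and Reimbursement for Time and Effort, including the three entry points in one section against two in another.

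1. State that the automated online surveys are outside the no-engagement rule.
2. Survey parents who enrolled and completed baseline before randomisation, in both arms, at 0, 2 and 4 months.
3. Restrict the between-arm parent self-report comparison to them. Randomisation need not be delayed: a parent whose baseline arrives later falls under item 4.
4. Report later-joining parents descriptively.

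If the rule is meant to cover surveys, say so, label parent self-report uncontrolled and descriptive, and remove it from the between-arm comparison.

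The cost is mainly wording, since the survey points are already reimbursed and the surveys already online. The downside is that the parent comparison rests on fewer, self-selected families, or is not made.

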Session 1 will be a 7-10 minute novella introducing participants to an ongoing story that will be continued for 8 weeks. The engaging story, created with a sophisticated health media company (MEE productions; http://www.meeproductions.com/, see above or Facilities) will show interactions between three Black adolescent males, their families, friends and potential sexual partners. Novellas will feature communication, relationships and behavior that are healthy and unhealthy. Novellas will be relevant to participants, seek to improve social support, and to provide motivation for, and modeling of, healthy behaviors. The novella will be suitable and engaging for both nHBAM and parents/caregivers, so the intervention provides a common ground for both. Content will be tailored for the adolescents and also for the parents/caregivers. Adolescents and parents/caregivers will have similar content (e.g. HIV/AIDS facts), but also content that is specifically for them (e.g. Peer pressure for adolescents and Effective parenting practices for parents). The online intervention can be viewed and completed by the adolescent and parent/caregiver on their own. Some novella content will encourage communication in the family, which we will assess at follow-up assessments.

The first text each week will be a continuation of the novella. The relevance of the topics

for that week and their healthy/unhealthy aspects will be shown in the novella. The second text will provide follow-up content to reinforce and amplify the message and allow time for personal reflection. Material will emphasize the knowledge, attitudes and behavioral message of the novella (the "take home messages"), which will be narrated by the novella characters. A brief novella clip will emphasize the point and/or the character will explain their thoughts, feelings or the anticipated consequences of their action. Each week, participants will chose a behavior ("practice exercise") that they can do in the next week. Practice choices of participants and their subsequent utility ratings may be tabulated and viewed online to reinforce "practice" and group participation.

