Nonheterosexual orientation: Because youth are enrolling in a project to promote Straight – Gay Acceptance, we anticipate that nearly all will be nonheterosexual, that is they will identify with at least one of the following categories: a) have had at least one non-coercive intimate sexual experience (e.g., prolonged kissing, oral sex, anal sex) with a male, b) expect to someday have a male sex partner, c) sexually aroused by and attracted to males, or d) selfidentify as gay, bisexual, gender-queer, or other term that is not heterosexual. In addition to determining feasibility and acceptability of MySTYLE, the purpose of the small RCT conducted is to determine effect size differences in knowledge, attitudes, and behaviors. Given the reality of effect decay and the constraints of the R34, we will use only two follow-up assessments at 2 and 4 months after baseline. Participants assigned to the waitlist control condition will also complete assessments at 6 and 8 months. Scale score outcomes include relevant knowledge (e.g. HIV/ STIs), attitudes (e.g. internalized stigma, condom attitudes) and behavior (e.g. prevention self-efficacy, parental monitoring of teens' activities and companions, and practice exercises) (see Appendix 2). Scales will be adapted for nHBAM from those used in STYLE or by our investigators. Table 1 summarizes our central measures, as a function of the Social Personal Framework, and others may be added as needed based on our formative work. **Behavioral outcomes** are: (1) the number of condomless sex acts during the follow-up period. (2) the rate of onset of sexual activity and (3) the acceptance of an HIV test. Sexual behaviors. HIV testing history and STI history will be assessed in a computer-assisted self-interview designed specifically for use with adolescents and using branching logic so that they only answer items that are relevant. (76-78) As a dependent variable, adolescents will be offered a free point-ofcare (POC) HIV test at 4. Also, self-report of prior HIV and STI testing will be assessed. Those who are not yet sexually active may decide against HIV testing and we will analyze the differences in testing rates separately based on self-report of sexual activity. Our outcome is testing, rather than the HIV or STI results because rates of infection will likely be low at this age, although the study will provide data on this issue in our high-prevalence city of Jackson, MS. Intervention content acceptability: At 2 or 6 months, depending on assigned condition, adolescents will complete the CSQ (see Year 2) to assess relevance and utility of the content and to aid in refinement of the intervention, if needed, prior to a subsequent, larger RCT.

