Analysis Plans for Aims 1 and 2 – see Formative Work earlier in this application. Analysis Plan (Aim 3). Enrollment will continue until 72 nHBAM are randomized Hypothesis: Among the 72 families enrolled with nHBAM, those in the MySTYLE will have fewer condomless sex acts (CSAs), a less onset of sexual activity, and greater HIV testing rates, compared with those in the waitlist control by the 4-month assessment. Further, those randomized to MySTYLE will have significantly greater levels of HIV prevention knowledge, more favorable attitudes toward HIV prevention, greater HIV prevention self-efficacy, and more effective family practices at 2- and 4-month assessments. Data will be aggregated across follow-up assessments and analyzed using generalized linear models. CSAs will be analyzed using a negative-binomial model, which will account for over-dispersion due to zero-inflation. HIV testing during the follow-up period will be assessed using a logistic model. Knowledge, attitude, and HIV risk scores will be evaluated at baseline, 2, and 4 months using linear mixedeffect models, which will account for the three assessments being nested within individuals, and will help mitigate bias due to missing data. (100, 101) We will test for differences in linear change over time between groups on each outcome variable. For HIV testing outcome, we will evaluate difference between conditions in the proportion of participants who engaged in HIV POC test. Propensity scores (i.e., inverse probability of treatment weighting) will be used to account for any imbalance in baseline characteristics between conditions. (102) Note that the research uses small block randomization based on age and sexual experience to reduce group imbalance. Intervention acceptability will be determined at the 2-month assessment using the Aim 2 criteria of mean scores ≥ 24 on the CSQ and ≥30 on the SEF.

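### MySTYLE's own practice exercises are listed as a between-arm scale outcome, but the waitlist has no valid value for them before month 4

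*Combined protocol and SAP*

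**What the plan says.** - **Outcome list (Measures for the Randomized Trial).** The paragraph opens its list with "Scale score outcomes include relevant knowledge (e.g. HIV/ STIs), attitudes" and ends the behavioural examples with "activities and companions, and practice exercises) (see Appendix 2". Practice exercises are thus one of the trial's scale-score outcomes. They are not among the three separately numbered behavioural outcomes (condomless sex acts, onset of sexual activity, HIV test acceptance).
- **Table 1, Family block.** The Parenting Practices entry includes a measure whose label begins "Intervention Practice" and continues with the word exercises, tagged for adolescent and parent.
- **What an exercise is (MySTYLE Intervention Condition).** "Each week, participants will chose a behavior", called a practice exercise, to carry out in the following week. Under Intervention fidelity and usage, the options sit on a page that cannot be reached until the MySTYLE video has played: "containing options for their weekly practice, etc.) until the video has fully played".
- **Waitlist access (RCT Phase, Format).** "Those participants assigned to the waitlist will be eligible to participate in MySTYLE after they have completed their 2- and 4-month assessments". The same paragraph says that staff do not engage the parent during the participant's four months on the waitlist.
- **Analysis (Analysis Plan, Aim 3).** "We will test for differences in linear change over time between groups on each outcome variable". The hypothesis includes better family practices under MySTYLE at 2 and 4 months.

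**The concern.** An efficacy outcome has to be something that either arm could show. Read by its label and by the plan's own definition, this item can be shown only by people who have been sent MySTYLE. A group difference in its change over time would then describe delivery of the programme, which is a feasibility result, and not a change in parenting or communication.

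Two things are at stake. Better family practices are part of the Aim 3 hypothesis, and Table 1 places this item with the parenting measures, so an apparent gain could be read as support for that hypothesis. The trial is also meant to supply effect sizes for a later R01 application, and a contrast that only records who was offered the exercises should not be among them.

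**Working it through.** **1. Which arm can have a value, and when**

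| Visit | MySTYLE arm | Waitlist arm |
|---|---|---|
| Baseline | No exercises yet offered | No exercises yet offered |
| 2 months | Eight weeks of exercises offered | None offered |
| 4 months | Exercises previously offered | None offered; access opens after this visit |

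The between-arm comparison uses exactly these three visits. For the parent form, the Format paragraph rules out contact with waitlist parents over the period. The reimbursement section does list online parent assessments at baseline, 2 and 4 months without excepting the waitlist, so those two places need reconciling. Either way, a waitlist parent has been sent no exercises.

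**2. What the planned test then gives**

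- Waitlist scored 0: the waitlist slope is 0 by construction, and the group difference equals the active arm's own uptake.
- Waitlist missing or not applicable: there is no waitlist slope, so the test cannot be run.

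**3. How the plan treats a comparable measure**

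The satisfaction questionnaire (CSQ) is given at 2 or 6 months according to arm, so each participant completes it after receiving the programme. Practice exercises depend on receipt in the same way, but have no such rule.

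**4. The plan's own yardstick**

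The Power section states a detectable effect of 0.41 SD (alpha 0.05, power 0.80, 72 enrolled, 85% retained). A simple two-group comparison, assuming 1:1 allocation and a two-sided test, gives:

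- N = 72 × 0.85 = 61.2, or 30.6 per arm: (1.960 + 0.842) × √(2/30.6) = 0.72 SD
- N = 72, or 36 per arm: (1.960 + 0.842) × √(2/36) = 0.66 SD

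Reaching 0.41 needs a within-person correlation of about 0.67 to 0.74 (baseline-adjusted mean of two follow-ups) or 0.81 to 0.84 (change score). The plan gives no correlation, so 0.41 can be neither confirmed nor refuted. It serves here only as the plan's own benchmark; the present point does not depend on it.

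**5. Illustration of size if the waitlist is scored 0**

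The plan gives no uptake figure, so everything here is assumed: 8 exercises, 30 analysed per arm, uptake varying between people as a beta-binomial with mean m and parameters summing to 2, and no effect on any real behaviour.

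Active-arm mean = 8m. Active-arm variance = 8m(1 − m)(1 + 7/3). Standardised difference = mean ÷ √(variance/2), because the waitlist variance is 0.

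| Uptake m | Mean | SD | Difference (SD units) | Simulated trials with p < 0.05 |
|---|---|---|---|---|
| 5% | 0.4 | 1.13 | 0.50 | 48% |
| 10% | 0.8 | 1.55 | 0.73 | 95% |
| 25% | 2.0 | 2.24 | 1.26 | about 100% |
| 50% | 4.0 | 2.58 | 2.19 | about 100% |

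Simulated mean differences (20,000 trials per row) were 0.52, 0.75, 1.27 and 2.21. As a cruder check, 6 of 30 active participants doing any exercise against 0 of 30 gives Fisher p = 0.024; 5 of 30 gives 0.052.

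The choice of denominator also matters. With an assumed mean of 4 and SD of 2.5, dividing by the active-arm SD gives 4/2.5 = 1.6, while pooling with a zero-variance arm gives 4/(2.5/√2) = 2.26. These figures show only that modest uptake could exceed 0.41 SD. They are not forecasts.

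**The case against.** The strongest reply is that the scoring is not visible. The plan says practice exercises, not completion of them, and refers to Appendix 2, which is not in the public file. An exercise is a behaviour, and the intervention section says that family communication encouraged by the novella will be assessed at follow-up. A form asking how often such behaviours occurred could be answered by either arm. This stands as a limit on certainty. It does not remove the point: the Table 1 label ties the measure to the intervention, the only definition given is a MySTYLE weekly task, and no waitlist version is described.

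It can also be said that the Aim 3 hypothesis does not name the item, that the mixed models are introduced for knowledge, attitude and HIV risk scores, and that no composite of family measures is defined, so the other scales would be read on their own. All of this is true and limits the consequence to one secondary scale outcome. The item is still listed as a scale-score outcome, and the test is stated for each outcome variable without exception. Its placement in the Parenting Practices row is a reading of a table whose rows are broken in the public text.

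Contamination does not supply a control value. Potential Challenges expects it to be mild, with links that cannot be forwarded.

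A reader might infer that the plan guarantees a false positive on family practices. The documents do not support that. A positive result follows only if the waitlist is scored 0 and uptake is more than minimal; if the waitlist is missing, no test exists. Nor do they support 1.6 SD, or any other figure, as the size of an artefact.

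**Conclusion.** As labelled and defined, practice exercises cannot estimate an effect of MySTYLE on parenting between baseline and month 4, because the waitlist has no valid value in that window. The contrast is either a record of who received the programme or absent. This conclusion rests on the outcome list, the Table 1 label, the definition of an exercise and the waitlist timing, and on no assumed number. It would change only if the Appendix 2 form asks about generic behaviours that both arms can report.

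The size of any artefact is unknown. The range of about 0.5 to 2.2 SD depends on a waitlist scored 0, assumed uptake of 5% to 50%, the assumed spread between people, and 30 analysed per arm. The reach is one scale outcome among several; the numbered behavioural outcomes and the other family scales are unaffected.

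**What to change.** - In Measures for the Randomized Trial, take practice exercises out of the scale-score efficacy outcomes. In Table 1, take them out of the Parenting Practices measures used for the Aim 3 comparison.
- Report them as uptake among MySTYLE recipients, alongside the videos viewed, minutes and replays already collected under Intervention fidelity and usage: the active arm in months 0 to 2, and waitlist participants who start MySTYLE after month 4.
- In the Aim 3 analysis plan, state that family practices are compared between arms with measures that both arms can answer, such as the adolescent versions of the PPM and the Parent-Adolescent Sexual Communication Scale.
- Keep the item as a between-arm outcome only if its form asks about generic behaviours reportable without having received MySTYLE. In that case, add a sentence saying how it is scored and that both arms complete it.

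The cost is a few lines of wording, with no new data and no change to sample size or to the stated power. The downside is that one apparently favourable outcome leaves the efficacy list.
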